### **Study exit**

The Study Exit table contains clinical information regarding the patient's study exit.

This table only contains two variables: the reason for leaving and the date of departure. Both variables will be adequately described by frequency of the reasons and the calculation, for their description and summary, of the corresponding waiting times.

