#### Annual follow-up (+/- 28 days):

5.- Variables during follow-up: anti-arrhythmic treatment, clinical recurrence of arrhythmia, result of the continuous ECG monitoring, 12-lead ECG, Nuubo monitoring method, etc. according to the protocol for each site.

A blanking period of 3 months has been established.

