#### 9.7. Data collection

The investigator and the members of his/her team must ensure the accuracy, integrity and authenticity of the data entered on the CRF. The sites will have the option to collect study data using the site worksheets, although the use of these is optional.

The data will be collected through an electronic data collection system for clinical trials. To facilitate the task of data collection, the sites will have paper copies of the sites' worksheets that contain the required information in accordance with the Clinical Investigation Plan for optional use in case the data are not captured elsewhere in the patient file. These will be stored in the study files.

The data entered on the CRF will come from the source documents and will be consistent with them. The investigation site team will create and store the source documents (such as the subject's clinical records, the ECGs, the subject's medical records, laboratory results, etc.). Only the persons authorized by the principal investigator may complete the CRF and only the investigator or designee authorized by the Principal Investigator may sign the CRF..

The Electronic Data Capture system maintains an audit trail on entries, changes or corrections in CRFs. If an individual authorized to complete the CRF makes changes to a CRF that has already been signed, the investigator must go sign the CRF again.

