## 9.9. Subject withdrawal or discontinuation

The study investigators can decide to remove the subject from the study in the following situations:

- Loss to follow-up over the course of the study. A patient will be considered as lost to follow after 3 attempts have been done to contact the patient without success and those are appropriately documented in the source documents
- Does not meet inclusion/exclusion criteria.
- The investigator thinks that it would be advisable for the subject to leave the study.

On the other hand, the subject has the right to terminate his/her participation in the study at any time during the course of the study.

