  - Congestive heart failure
  - Hemorrhagic events without stroke
  - Myocardial infarction
  - Stroke
  - Arrhythmia: atrial flutter or inappropriate sinus tachycardia or sinus dysfunction after the blanking period
  - Recurrence of AF or left flutter after the blanking period

Note: The cases of recurrence of AF and the hospitalizations arising from AF will be collected in the adverse event form even though they will be processed as part of the analysis of the efficacy and not safety variables.

The investigator has to specify on the eCRF whether an adverse event can be deemed to be serious or not. If the adverse event meets any of the following criteria, it is considered a serious adverse event (SAE):

- Led to death
- Caused serious deterioration in the subject's health that has:
  - a) resulted in a life-threatening illness or injury, or
  - b) resulted in a permanent impairment of a body structure or a body function, or
  - c) required in-subject hospitalization or prolongation of existing hospitalization, or
  - d) resulted in medical or surgical intervention to prevent life threatening illness or injury or permanent impairment to a body structure or a body function.

Note: Planned hospitalization for a pre-existing condition is not considered a serious adverse event.

Note 2: Hospitalization is defined as patient staying overnight at the hospital (more than 24h)

The investigator also has to evaluate on the eCRF whether there is a reasonable possibility that the device may have caused or contributed to an AE. The factors that could be considered are time relationships, biological plausibility, the association (or lack of association) with the underlying disease and the presence (or absence) of a more likely cause. If an adverse event is classiffied as potentially related to the device this should be also notififed following the regular communication channels of the vigilance system.

All the data collected relating to adverse events will be reviewed remotely to ensure the correct reporting and classification of the event. In the event of having doubts about the classification and relationship with the device established by the investigator, the Scientific Committee will be consulted.

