## **Follow-up**

The Follow-up table contains clinical information related to the follow-up of the patient. At the time of writing this protocol, it is unknown whether a patient can have multiple follow-up visits.

Continuous variables will be described using the statistics of central tendency (mean and median), dispersion (minimum, maximum, standard deviation and interquartile range) and shape (skewness and kurtosis). The number of valid cases and the number of cases with missing values will be reported. The continuous variables in this table are: Date of the follow-up visit, Date of post-procedure discharge, Date of admission, Date of discharge, Number of hospital stays.

The categorical variables will be described by frequencies and percentages. The number of valid cases and the number of cases with missing values will be reported. The categorical variables contained in this table are: Follow-up visit, ECG record / Monitoring type, Recurrence 3 months post-procedure, Recurrence specification, Asymptomatic AF, Treatment, Antiarrhythmics, Antiarrhythmic type, Specify, Anticoagulants, NACOs type, REDO, Type REDO, Death, Hospital stay

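### For subjects who leave before the annual visit, the plan secures only adverse-event entries and the exit reason and date, so a leaver with no recorded recurrence can be carried forward as AF-free without evidence of monitoring

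*SAP*

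**What the plan says.** **Exit.** The SAP's Study exit section states: "This table only contains two variables: the reason for leaving and the date of departure". In Protocol Table 1, Study Exit is completed when it occurs and triggers no other form.

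**Loss.** Protocol 9.9 states: "A patient will be considered as lost to follow after 3 attempts have been done to contact the patient without success". The attempts must be documented, but no search of the site's records is asked for. Removal is discretionary: "The study investigators can decide to remove the subject from the study in the following situations".

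**Follow-up data.** Protocol 9.1 schedules an annual follow-up with a window of 28 days either side, and Table 1 places the AF monitoring test under Follow-up only. The categorical variables of the SAP's Follow-up table begin: "Follow-up visit, ECG record / Monitoring type, Recurrence 3 months post-procedure, Recurrence specification, Asymptomatic AF, Treatment, Antiarrhythmics". Redo and death come later in that list. No date of recurrence or of last rhythm recording is among the variables. On the number of visits the SAP says: "At the time of writing this protocol, it is unknown whether a patient can have multiple follow-up visits".

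**Adverse event route.** Protocol 11.2 states: "The cases of recurrence of AF and the hospitalizations arising from AF will be collected in the adverse event form". These entries are treated as efficacy data and are due before 10 calendar days from awareness. The SAP (Statistical models) takes recurrence from both the Follow-up and the Adverse Event tables.

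**Source of data.** Protocol 9.7 states: "The data entered on the CRF will come from the source documents and will be consistent with them". It names clinical records and ECGs among the source documents.

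**Missing data.** The SAP (Treatment of missing values) carries the last valid status forward where the passage of time matters. Its example covers both a subject without an event and one with no information at database closure.

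**The concern.** The adverse event form records positive findings. It has no field for a subject who was monitored and found free of AF, none for the type of monitoring, and none for the date of the last recording. An early leaver with no event entry may have had several clean Holter recordings or no rhythm test at all, and the database cannot tell the two apart.

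Two analyses depend on that distinction. Under the carry-forward rule, the primary percentage can count such a leaver as AF-free at 12 months. The Kaplan-Meier description needs the date on which a subject was last known to be free of recurrence. The exit date is a poor substitute, because nothing shows that rhythm was assessed up to that day.

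The loss rule adds to this. In a registry that takes its data from routine records, an unanswered call does not mean that no outcome exists. A subject with a 12-month ECG or Holter in the site's files can still be coded lost. About 30 sites may handle such cases differently.

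**Working it through.** The plan states no loss rate, expected success rate or precision target, so there is no figure to reproduce. The check has two parts.

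**1. What is assured for a subject who leaves before the annual visit**

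The earliest in-window visit is day 365 - 28 = 337. For an exit before then:

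| Item | Assured? | Where |
|---|---|---|
| AF recurrence after blanking, if known to the site | Yes, as an adverse event | Protocol 11.2 |
| AF hospitalization, death | Yes, as adverse events | Protocol 11.2 |
| Exit reason and date | Yes | SAP, Study exit |
| Rhythm recording without AF | Not required | Follow-up form only |
| Monitoring type | Not required | Follow-up form only |
| Antiarrhythmics and redo during follow-up | Not required | Follow-up form only |
| Date of last rhythm recording | Not listed on any form | - |

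**2. Possible size (all rates are assumptions)**

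Let *c* be the AF-free proportion among completers, *d* the proportion leaving early, and *u* the share of leavers with a recurrence not filed as an adverse event. The other leavers are taken as AF-free.

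- True proportion: (1 - d)c + d(1 - u)
- Leavers carried forward as AF-free: (1 - d)c + d. Overstatement: d × u
- Leavers excluded from the denominator: c. Overstatement: d(c + u - 1)

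With c = 0.80:

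| d | u | True | Carried forward | Overstatement | Excluded | Overstatement |
|---|---|---|---|---|---|---|
| 5% | 25% | 0.76 + 0.0375 = 79.75% | 0.76 + 0.05 = 81.0% | 1.25 points | 80.0% | 0.25 points |
| 15% | 40% | 0.68 + 0.09 = 77.0% | 0.68 + 0.15 = 83.0% | 6.0 points | 80.0% | 3.0 points |

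The carried-forward overstatement, d × u, does not depend on c. The excluded one does.

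**Dependence on adverse event capture.** Let *r* be the share of leavers who recur and *k* the share of those recurrences that reach the adverse event form. The carried-forward overstatement is d × r × (1 - k). With d = 10%, r = 50% and c = 80%, the true value is 0.72 + 0.05 = 77.0%. The reported value is:

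- k = 0: 82.0% (5.0 points too high)
- k = 0.5: 79.5% (2.5 points too high)
- k = 1: 77.0% (no error)

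**Comparison with sampling error.** At N = 1000 and 80%, the 95% half-width is 1.96 × √(0.8 × 0.2 / 1000) = 2.5 points.

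**Bounds.** If nothing is known about leavers, the primary percentage can lie anywhere from (1 - d)c to (1 - d)c + d, a width equal to the exit rate. With c = 80% this is 76.0-81.0% at 5% exit, 72.0-82.0% at 10% and 64.0-84.0% at 20%.

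**The case against.** A reader might infer that rhythm data for early leavers are never entered. The documents do not support that. Recurrences, AF hospitalizations and deaths known to the site go on the adverse event form as they occur and feed the primary endpoint. This part of the objection stands, and the gap is confined to negative and contextual information.

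A reader might also take a single follow-up visit as settled. It is the natural reading of Protocol 9.1, but the SAP leaves the number open and the protocol allows follow-up to be extended. Nor do three failed contacts bar data entry. Removal is a choice, and no text forbids completing a Follow-up form from the records at or before exit. The plan is silent here, which is different from excluding the data.

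It would be too strong to say that Kaplan-Meier cannot be run. Event and exit dates both exist, so every subject has a time. What is missing is assurance that AF-free time up to exit was observed.

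The size can fairly be challenged. It assumes that sites fail to file recurrences they are told to file, and much of the harm comes from the carry-forward rule. Both points are accepted, and the figures are therefore conditional. It can also be said that a descriptive registry with no power target can live with this. But its primary result is a single percentage, and the plausible shift can match or exceed its sampling error.

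**Conclusion.** The concern holds in limited form. For early leavers the plan assures reportable adverse events and the exit reason and date. It does not require the information that separates a subject monitored and free of AF from one who was not monitored. With the carry-forward rule, the second can be counted as the first.

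The size is unknown. With 5-15% leaving early and 25-40% of them having an unfiled recurrence, the AF-free percentage is overstated by 1.25 to 6 points if leavers are carried forward. If leavers are excluded and 80% of completers are AF-free, it is 0.25 to 3 points. It is about nil if every recurrence up to month 12 reaches the adverse event form. None of these rates comes from the documents. This is a cheap improvement worth making, because it replaces a stated loss rule and secures data that the plan does not now secure. It is not evidence that the primary result will be wrong.

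**What to change.** **Protocol 9.1, 9.9 and Table 1**

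1. When a Study Exit form is opened before the annual visit, and unless consent is withdrawn, complete the Follow-up form from source documents up to the exit date. Add fields for the date of recurrence and the date of the last rhythm recording.
2. Before coding a subject lost, check the site's records as well as attempting contact. If they hold a rhythm recording in the 12-month window and consent is not withdrawn, complete the annual form from them. Record the monitoring type, so that a brief ECG is not read as equal to prolonged monitoring.

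**SAP, Treatment of missing values and Statistical models**

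3. Censor early leavers without recurrence at the last rhythm recording, and do not carry AF-free status forward to 12 months.

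**Cost.** A chart check by the site for each early leaver, one or two added eCRF fields, a rule that opens the Follow-up form at exit, and a few lines of text. No new visit or test is needed.

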### **Statistical models**

In order to conclude on the primary objective of the study, the number and percentage of cases with absence of atrial fibrillation recurrences will be calculated after 12 months of follow-up, after the cryoablation procedure. The scientific coordinators of the study will have to determine the closing date of the database so that it has been possible to collect information from 12 months of follow-up of a sufficiently large number of patients.

The protocol defines AF recurrence as a clinically diagnosed and documented episode of AF (using ECG, Holter monitor with a duration of at least 30 seconds, or using implantable devices

or event monitoring systems). The information necessary to determine the existence of a recurrence of AF will be extracted from the Follow-up and Adverse Events tables.

The existence of differences between patients with and without recurrence in clinical variables and patient follow-up will be explored. Student's t statistics (for continuous variables) and  $\chi^2$  (for categorical variables) will be used. If there are appreciable differences between the groups of patients in the clinical variables, logistic regression models will be proposed to study the multivariate effect of the variables and assess their predictive capacity.

The waiting times until the moment of recurrence of AF will be described using survival models (survival tables and Kaplan-Meier) and the existence of variables capable of predicting the differences between both groups of patients will be explored.

The necessary statistical analyzes will be approached to verify the secondary objectives based on the variables designated by the study coordinators.

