# 5. Study objectives and endpoints

## 5.1. Objectives

#### **5.1.1.** Primary Objective

To evaluate the efficacy of the cryoablation procedure at 12 months, defined as the absence of recurrences of atrial fibrillation.

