# 9. Study Procedures

It is an observational study whereby the participating sites will carry out the cryoablation procedure in accordance with standard practice at their site. During this baseline procedure and during follow-up, there are no related additional tests and only the data deemed necessary according to the Case Report Form will be collected.

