# 13. Statistical design and methods

The following statistical analysis plan of the data will be carried out:

The variables analyzed will be those collected in the subject registry corresponding to the different protocols of the procedure, intervention data, complications, follow-up and long-term results in these subjects. In the Method section there is a list of variables of interest.

Recurrence of AF will be defined as a clinically diagnosed episode of AF and accordingly documented (on ECG, Holter monitor with a duration of at least 30 seconds or implantable devices or event recording systems).

It is expected to carry out 3 analyses of the primary and secondary objectives described in the Clinical Investigation Plan:

- 1. At the end of the first year of enrollment
- 2. At the end of the second year of enrollment
- 3. At the end of follow-up

On the other hand, there will be 4 analyses of additional proposals throughout the study (see Appendix B: Publications Plan)

- Two analyses at the end of enrollment.
- Two analyses at the end of follow-up.

Each of the variables of interest will be described univariantly and individually.

Crosses of variables will also be carried out to describe each one of the clinical strata of interest.

When it is possible and of interest for the investigators, statistical comparisons between strata will be carried out through statistical tests.

Specific statistical models to respond to the interests of the investigators will be proposed, such as comparison of the procedures or comparison of subject strata.

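### A subject followed up with no rhythm recording can be counted as free of AF recurrence, and the plan neither rules this out nor reports how many such subjects there are

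*SAP*

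**What the plan says.** The primary objective (protocol 5.1.1) is "To evaluate the efficacy of the cryoablation procedure at 12 months, defined as the absence of recurrences of atrial fibrillation". The SAP, under Statistical models, turns this into a simple proportion: "the number and percentage of cases with absence of atrial fibrillation recurrences will be calculated after 12 months of follow-up". It gives no denominator and no rule for who is evaluable.

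Only the positive event is defined. Protocol section 13 states: "Recurrence of AF will be defined as a clinically diagnosed episode of AF and accordingly documented", and lists ECG, Holter, implantable devices and event recorders as the means. The SAP repeats this ("The protocol defines AF recurrence as a clinically diagnosed and documented episode of AF") and adds: "The information necessary to determine the existence of a recurrence of AF will be extracted from the Follow-up and Adverse Events tables". Neither document defines absence of recurrence.

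On monitoring, protocol section 9 says that at follow-up "there are no related additional tests and only the data deemed necessary according to the Case Report Form will be collected". The annual follow-up entry lists several kinds of rhythm monitoring, to be done "according to the protocol for each site", and sets a 3-month blanking period. Table 1 marks an AF monitoring test at follow-up. In the SAP's Follow-up table, "ECG record / Monitoring type" and recurrence from three months after the procedure are separate categorical fields.

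The SAP's section on missing values has two relevant rules. Non-response is first treated as missing completely at random, variable by variable. Where measurements are repeated or time matters, the last valid status is carried forward, and the worked example includes a subject with no information on the event when the database closes.

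**The concern.** The endpoint asks for evidence on one side only. A failure needs a diagnosis and a tracing or device record. A success, as the text stands, needs only that no such record exists. In a registry that adds no tests, a subject can come to the annual visit, report no symptoms, have no recording after blanking, and still contribute to the numerator. The Follow-up table also has a field for asymptomatic AF, so the registry itself recognises AF that a visit without a recording would not show.

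At stake is what the headline percentage can claim. If an appreciable share of subjects were never recorded, part of the reported efficacy is absence of information. The same classification feeds the SAP's comparison of subjects with and without recurrence, its logistic models and its Kaplan-Meier description.

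**Working it through.** **How an unrecorded subject passes through the plan.** The subject attends, has no recording after blanking, and has no recurrence on file.

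1. *Recurrence field answered no on clinical grounds.* No value is missing, so neither missing-value rule applies. The subject counts as free of recurrence.
2. *Recurrence field blank, carry-forward applied.* The subject keeps the last valid status. With no recurrence on file, that status is free of recurrence.
3. *Recurrence field blank, completely-at-random rule applied.* The subject leaves the denominator.

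The SAP does not say whether rule 2 or rule 3 governs the primary percentage. Two of the three routes end in the numerator.

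**Inputs.** The plan has no figure to reproduce: the sample of about 1000 rests on procedure volume (protocol 8.1), with no expected rate, precision or dropout. The following are assumptions.

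- *u*, the share of attending subjects with no recurrence on file and no recording: 5-20%.
- *p*, the share without recurrence among the others: 70-80%.
- *r*, the true recurrence proportion among the unrecorded: 20-30%, that is, equal to 1 − p.

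**Formulas.**

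- A, unrecorded counted as AF-free: (1 − u)p + u
- B, unrecorded counted as recurred: (1 − u)p
- C, unrecorded excluded: p
- Overstatement of A against the truth: u × r, which is never negative
- Width of the bounds: A − B = u

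| p | u | A | B | C |
|---|---|---|---|---|
| 80% | 5% | 81.0% | 76.0% | 80.0% |
| 80% | 10% | 82.0% | 72.0% | 80.0% |
| 80% | 20% | 84.0% | 64.0% | 80.0% |
| 70% | 5% | 71.5% | 66.5% | 70.0% |
| 70% | 10% | 73.0% | 63.0% | 70.0% |
| 70% | 20% | 76.0% | 56.0% | 70.0% |

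The smallest overstatement is 0.05 × 0.20 = 1.0 point and the largest is 0.20 × 0.30 = 6.0 points.

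**Against sampling error.** At p = 70% and n = 1000 the 95% half-width is 1.96 × √(0.70 × 0.30 / 1000) = 2.8 points. The overstatement reaches that at u of about 9.5% (12.4% if p = 80%). With fewer than 1000 subjects at 12 months the half-width is somewhat larger, for example 3.2 points at n = 800.

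**If unrecorded subjects recur half as often.** Take p = 70% and r = 15%. The true percentage is (1 − u) × 0.70 + u × 0.85.

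- u = 10%: truth 71.5%; A is 1.5 points too high and C is 1.5 points too low.
- u = 20%: truth 73.0%; A is 3.0 points too high and C is 3.0 points too low.

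The overstatement in A keeps its sign but halves, and excluding these subjects is then biased the other way.

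**The case against.** Four points can be made for the plan.

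- *The SAP never says that unrecorded subjects are AF-free.* This is correct. It follows from the one-sided definition, together with carry-forward where the recurrence field is blank, and the completely-at-random rule could instead drop a blank field. A reader might infer that the SAP prescribes counting them as successes; the text leaves it open.
- *Table 1 lists an AF monitoring test at follow-up under data collection requirements.* A reader might infer from the one-sided definition that monitoring is not expected at all, and this entry tells against that. But section 9 adds no tests and the follow-up entry defers to site practice, so it can be read as collect if done. Nothing makes it a condition for counting a subject AF-free.
- *The SAP already reports valid and missing counts for each Follow-up field.* The amount of missing monitoring data will therefore be visible. It will not be crossed with recurrence status, which is the count that matters here.
- *Requiring a recording could do harm.* A reader might infer that the primary denominator should be limited to recorded subjects. The documents do not support that as the clear choice. Recurrences are documented by definition, so exclusion removes only non-recurrent subjects, and the result is biased downward if symptoms prompt recording. This objection stands, and the fix below respects it.

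A related limit: one ECG shortly after blanking would count as a recording. How intensively sites monitor, which protocol 4.2 acknowledges varies widely, is a wider matter that this point does not settle.

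**Conclusion.** The concern holds in a limited form. As written, the plan allows a subject who attends with no recording to be counted as free of AF recurrence, and each such count raises the primary percentage or leaves it unchanged. The direction is fixed; the size is not known. The range of 1 to 6 points depends on an assumed 5-20% unrecorded and 20-30% recurrence among them. It shrinks if unrecorded subjects recur less often, and it is zero if every subject is recorded or no unrecorded subject recurs. A reader might take it as established that the result is inflated by that amount; the documents give neither input, so they do not show it. What they do show is that the percentage cannot be interpreted without the number of unrecorded subjects, and the plan does not commit to reporting that number beside it.

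**What to change.** In the SAP's primary analysis:

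1. State that the carry-forward rule in the missing-value section does not establish AF-free status.
2. Use "ECG record / Monitoring type" with the follow-up visit date to flag subjects who have no documented recurrence and no recording at follow-up after blanking. The flag also needs the procedure date and the recurrences in the Adverse event table. Name this merge, because the SAP otherwise analyses its tables separately.
3. Report the number flagged next to the primary percentage.
4. Give the percentage three ways: flagged subjects counted as AF-free, counted as recurred, and excluded as not assessed.
5. Describe the main figure as *no documented recurrence*, and note that the recorded-only figure may be too low if recording is prompted by symptoms.

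This adds no test or visit. The cost is a little more analysis and a wider reported range. One limitation remains: the SAP lists no recording date in the Follow-up table, so whether a recording fell after blanking may have to rest on the visit date.
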